Thus, good evidence suggests that at least acute treatment with ARBs could ameliorate lung injury in COVID-19. We therefore propose to test losartan in a Phase I proof of concept and safety trial. The primary hypothesis to be tested is that losartan treatment is safe in the setting of acute SARS-CoV-2 infection. Secondarily, losartan can potentially reduce the length of respiratory failure due to SARS-CoV-2.

Significance

Importance of the problem: As outlined above, there is currently no data that supports specific treatment options for respiratory failure in COVID-19. There are active or soon to be active clinical trials that may show promise in this space such as blocking IL-6 with tocilizumab²⁰ or using hydroxychloroquine. None of these therapies are without side effects and alternative or additional approaches could lessen the burden of respiratory failure in this patient population.

Approach and Protocol

This is an open label, phase 1 clinical trial to evaluate the safety of losartan in respiratory failure due to COVID-19.

Clinical Trial setup:

Detailed inclusion and exclusion criteria are listed below. Briefly, 50 patients with COVID-19 and respiratory failure who meet criteria and agree to participation in the study will be placed on losartan 25 mg daily on study day 0. If parameters are met the dose of losartan will be increased to 50 mg on study day 3. Participants will continue losartan until they experience resolution of respiratory failure (normal oxygen levels on room air), are discharged from the hospital, meet stoppage criteria (detailed below) or complete 14 days of therapy.

Primary hypothesis and endpoint:

- Losartan is safe in acute respiratory failure due to SARS-CoV-2.

Secondary endpoints:

- Losartan reduces the number of days on supplemental oxygen in respiratory failure due to COVID-19
- Incidence of mechanical ventilation use
- Days on mechanical ventilation
- Incidence of non-invasive positive pressure ventilation or heated high flow nasal cannula use
- Days on non-invasive positive pressure ventilation or high flow nasal cannula
- Incidence of transfer to ICU from non-ICU hospital bed
- ICU length of stay (days)
- In-hospital mortality
- Hospital length of stay (days)
- Cumulative incidence of severe adverse events
- Cumulative incidence of adverse events
- Change from baseline in oxygenation

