- Monitor subject for safety and losartan stoppage criteria.
- For participants following inclusion criteria #5: Day 0 assessments should be performed on enrollment day as well as day 1 **or** day 2 based on first dose of SOC losartan administration.

Day 3:

- Dose escalation: On study day 3 if none of the parameters listed below are met the dose of losartan will be increased to 50 mg once daily.

Day 4 until study completion:

- Monitor subject for safety and losartan stoppage criteria.
- Treatment group will have nasopharyngeal swab and research plasma collected at end of study.

Stoppage criteria for losartan

- Hyperkalemia (persistent values >5.5 mM recorded on at least 2 readings).
- Worsening renal function (Cockcroft-Gault <30 mL/min/1.73 m²) or urinary output <20 mL/h.
- Skin rashes, palpitations or other moderate or severe adverse events (interference with usual daily activities) without clear explanation should warrant immediate cessation of treatment and notification of study personnel.
- Development of sustained hypotension defined as SBP <90 mmHg, DBP <60 mmHg recorded on at least two readings 30 min apart or use of norepinephrine >0.1 µg/kg/min.

[figure not shown]
- Any change in monitor lab parameters deemed significant and potentially related to study drug by the Investigator.

Dose de-escalation criteria

- Any change in monitoring parameter after dose increase from 25 mg to 50 mg that is considered significant by the investigator will trigger a decrease dose back to 25 mg
- If abnormal parameter is resolved and, in the opinion of the investigator, is unlikely to be related to losartan will increase dose back to 50 mg
- If de-escalation criteria is met after re challenging 50mg dose, the dose will be once more decreased to 25mg until the end of the study.

Criteria for resuming after stopping

- If stoppage criteria have resolved and reason for stoppage is felt to be unlikely or possibly related to losartan, discussion of resumption of losartan with medical monitor
- Dose resumption will start at 25 mg. If stopped at 25 mg → the dose will be continued for three days followed by increase to 50 mg if tolerated. If stopped at 50 mg, 25 mg will be started and escalated to 50 mg the day after if tolerated.

Control

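### At 50 mg the stop rule and the reduce-to-25 mg rule overlap for drug-related lab changes, and the relatedness condition for returning to 50 mg is looser after a stop than after a reduction

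*Combined protocol and SAP*

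**What the plan says.** The dosing rules are in three consecutive sections of the protocol.

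- **Stoppage criteria for losartan.** Besides numerical limits for potassium, renal function and blood pressure, and a criterion for unexplained moderate or severe adverse events, losartan is stopped for "Any change in monitor lab parameters deemed significant and potentially related to study drug by the Investigator". This criterion applies at either dose.
- **Dose de-escalation criteria.** The trigger is "Any change in monitoring parameter after dose increase from 25 mg to 50 mg that is considered significant by the investigator", and the action is a return to 25 mg. The condition for going back up is "If abnormal parameter is resolved and, in the opinion of the investigator, is unlikely to be related to losartan". If the criteria are met again after re-challenge, "the dose will be once more decreased to 25mg until the end of the study".
- **Criteria for resuming after stopping.** Once the stoppage criteria have resolved, the condition is that the "reason for stoppage is felt to be unlikely or possibly related to losartan, discussion of resumption of losartan with medical monitor". On the dose path: "If stopped at 50 mg, 25 mg will be started and escalated to 50 mg the day after if tolerated".

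Clinical Trial setup says that participants continue until they recover from respiratory failure, or "are discharged from the hospital, meet stoppage criteria (detailed below) or complete 14 days of therapy". The Losartan section also lists stoppage criteria among the end points of therapy. Table 1 attaches a stop instruction to many adverse event grades. None of its rows mentions a dose reduction.

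**The concern.** There are two separate problems.

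First, one event can attract two dose orders. The reduction rule asks only whether a change after escalation is significant. It has no relatedness condition and no exception for stop events. Whether a participant with a significant, potentially related lab change comes off losartan or stays on 25 mg therefore depends on how staff read the sections together.

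Second, the return rules run the wrong way round. The reasons for stopping include sustained hypotension and worsening renal function, and the Losartan section names hypotension and renal dysfunction among the drug's serious adverse events. Yet an event leading to a stop may be possibly drug-related and still be followed by 50 mg, while an event leading only to a reduction must be unlikely to be related.

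The primary hypothesis is safety, and intolerance of 50 mg after tolerating 25 mg is a secondary endpoint. Different readings of these rules change exposure at 50 mg and may change how intolerance is recorded. The documents give no basis for quantifying that effect.

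**Working it through.** The plan gives no figure to reproduce. The check is a comparison of conditions, followed by a small illustration.

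**Step 1: do the triggers overlap?**

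- Stop (last criterion) = lab change AND significant AND potentially related, at any dose.
- Reduce = monitored change AND significant AND after escalation to 50 mg.

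Every lab change at 50 mg that is significant and potentially related satisfies both, and the actions differ (stop; 25 mg).

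**Step 2: does Table 1 settle the order?** Only in part. It has 10 rows, 7 of them for labs. In 5 lab rows the first stop instruction is at Grade 2 (leukocytes, platelets, potassium, liver enzymes, CPK), with a repeat value asked for in the potassium footnote. In 2 rows (hemoglobin, creatinine) it is at Grade 3. At Grade 2 in those two rows the table gives only follow-up, so it does not choose between stopping and reducing.

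The numerical renal limit need not decide the matter either. Cockcroft-Gault clearance is inversely proportional to creatinine, so with an assumed baseline of 80, a doubling of creatinine (Grade 2) gives 80 / 2 = 40, above the stop limit of 30. If that change is judged significant and potentially related, the two dose rules still both apply.

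**Step 3: compare the return rules, granting stop-first in full.**

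| | After a reduction | After a stop at 50 mg |
|---|---|---|
| Resolution required | Yes | Yes |
| Relatedness accepted | Unlikely only | Unlikely or possible |
| Who is involved | Investigator | Discussion with medical monitor |
| Path to 50 mg | Directly | 25 mg, then 50 mg next day if tolerated |
| Re-challenge limit in that section | One | None stated |

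With stop-first, the contrast is between different events. Potentially related lab changes all go to the stop route. A possibly related non-lab change that meets no stop criterion goes to reduction: for example, a blood pressure fall judged significant that falls short of "Development of sustained hypotension defined as SBP <90 mmHg, DBP <60 mmHg recorded on at least two readings 30 min apart". The lesser fall does not meet the condition for returning to 50 mg; the sustained hypotension can.

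**Step 4: illustration of size.** Assumptions: dosing days 0 to 13, event found before the dose on day e, k days off drug, event possibly related, restart agreed and tolerated, no earlier discharge or recovery.

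- If interruptions count toward the 14 days, further days at 50 mg after a stop = 13 − e − k. For e = 6 and k = 2, 3, 4: 5, 4, 3 days.
- If only dosed days count, 14 − 6 = 8 doses remain, one of them at 25 mg, leaving 8 − 1 = 7 days at 50 mg.
- After a reduction on day 6: 14 − 6 = 8 days at 25 mg and 0 at 50 mg.

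The event day and k are assumed, so these counts show scale only.

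**The case against.** The strongest reply is that the plan already works. The lab stop criterion is the narrower rule, other sections make stoppage criteria end therapy, and under either rule the participant leaves 50 mg at once. A figure is missing from the extracted text inside the stoppage list, and the Study procedures heading points to a schematic, so an order may be drawn there. All of this stands. A reader might infer that the plan has no order between the rules; the documents do not support that. What can be said is that the wording of the reduction rule does not exclude stop events.

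The return rules can also be defended. After a reduction the investigator alone may re-escalate, so a stricter condition fits. After a stop there must be resolution, a discussion with the medical monitor, a 25 mg restart and tolerance. The extra oversight is real. But the text gives the monitor no stricter criterion, and oversight does not explain why the relatedness condition should be wider after the more serious event.

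Three further readings are tempting and not supported:

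- **Unlimited re-challenge after a stop.** The resuming section states no limit. However, the rule holding participants at 25 mg to the end of the study can be read to cover any re-challenge at 50 mg, each resumption needs discussion with the monitor, and Safety Reporting and Removal of Subjects from Study provide for withdrawal.
- **Three conflicting orders for Grade 2 creatinine.** Close follow-up is compatible with stopping or reducing. It is not a third dose order.
- **An outright ban on 50 mg after a possibly related reduction.** This follows from the stated condition not being met; no explicit prohibition is written.

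**Conclusion.** The point holds in a limited form. On the wording, a significant, potentially related lab change at 50 mg meets two rules with different actions. Stop-first is the sensible reading and is implied elsewhere, but the reduction rule should say it. Independently of that, the stated relatedness condition for returning to 50 mg is looser after a stop than after a reduction, and this is the more important part because it concerns repeat exposure after hypotension or renal decline.

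The size is modest: in the day-6 example, 3 to 5 further days at 50 mg against none, or 7 if interruptions do not count toward the 14 days. Return after a stop is permitted, not automatic. The overlap would be a matter of wording only if the missing figure shows stop-first. This is a safety rule that should be corrected; it does not touch the sample size or power.

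**What to change.** Make both changes together in the dosing rules under Study procedures.

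1. In Dose de-escalation criteria, state that any stoppage criterion, or any Table 1 grade whose action is to stop losartan, overrides the reduction rule (keeping the repeat value for potassium). Reduction then applies only to significant changes that meet neither.
2. In Criteria for resuming after stopping, state that after a stop at 50 mg the dose returns to 50 mg only if the cause has resolved and is unlikely to be related, with the same single re-challenge limit as after a reduction. If the cause is possibly related, the participant resumes at 25 mg after discussion with the medical monitor and stays there.

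The re-challenge limit in item 2 has to be explicit: once item 1 takes stop events out of the reduction rule, the 25 mg cap in the de-escalation section could no longer be read to cover them.

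The cost is about two sentences, with no new data or visits. The downside is fewer days at 50 mg, and so less information at that dose, for participants whose stop was possibly related.

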- Incidence of medications with possible antiviral activity (hydroxychloroquine, lopinavir/ritonavir, ribavirin or remdesivir) or adjunctive therapy use (e.g., tocilizumab)
- Incidence (and length in days) of extracorporeal membrane oxygenation use
- Incidence (and length in days) of renal replacement therapy use
- Intolerance of high dose (50mg) losartan after tolerating 25mg
- Change in SARS-CoV-2 viral load determined by quantitative PCR

Inclusion criteria:

1. Age ≥ 18 years admitted to the University of Kansas Health System.
2. Confirmation of infection with SARS-CoV-2 by PCR testing.
3. Hypoxic respiratory failure
 - Requiring mechanical ventilation or oxygen OR a SpO₂ $\leq 94\%$ on room air or a P_aO₂/F_iO₂ (P/F) ratio <300 OR tachypnea (respiratory rate ≥ 24 breaths/min).
4. Other concomitant medications such as antivirals and hydroxychloroquine are allowed.
5. Participants prescribed standard of care (SOC) losartan (25mg QD) within 48 hours of consenting may be considered for enrollment if eligibility criteria are met based on EMR data assessment, i.e. no other ARB or ACE prior to SOC medication administration. If participant is eligible and signs consent form, investigational losartan 25mg QD will be ordered to replace SOC prescription on the following scheduled dose.

Exclusion criteria:

1. Pregnancy.
2. Respiratory failure due to a process other than COVID-19.
3. Intolerance to ARBs.
4. Previous treatment with an ARB or ACE inhibitor (see exception in inclusion criteria).
5. Current chronic use of medication with known interactions with losartan including NSAIDs (intermittent prior use is acceptable), potassium supplementation aliskiren.
6. Blood pressure less than 90 mm Hg systolic or 60 mm Hg diastolic recorded on at least two readings 30 min apart.
7. Need for vasopressors, unless norepinephrine ≤ 0.1 μ g/kg/min
8. Hyperkalemia (serum K⁺ > 5.5 mM).
9. Known cardiac failure (left ventricular ejection fraction $\leq 35\%$), renal insufficiency (Cockcroft-Gault < 30 mL/min/1.73 m² or urinary output < 20 mL/h), hepatic failure (LFTs > 5 x normal upper limit).
10. Known renal artery stenosis.
11. Neurological, psychiatric, endocrine or neoplastic diseases that are judged to interfere with participation in the study.
12. On another interventional trial (including one for COVID-19) that excludes participation.
13. Meeting all inclusion criteria for more than 48 hours prior to Day 0

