Patients that request to not be treated with Losartan will be approached by the study team to request permission for their standard of care treatment and data be followed and recorded by the research team for this study. Patients that agree, will sign the consent form, but will not provide a blood sample for research. We will also collect medical information relating to safety criteria on historical controls treated at the University of Kansas Hospital in the 30 days prior to the study start date (3/25/2020) and during the study period. These controls will be retrospectively identified through query of the electronic health record. We will attempt to include controls that meet all criteria for enrollment into the study but to achieve a ratio of controls to study participants of 2:1 may need include some with exclusion criteria (excluding prior ACE inhibitor or ARB use). Controls identified retrospectively will not undergo informed consent as this represents minimal risk.

Losartan

Losartan is an FDA-approved ARB widely prescribed for treatment of hypertension, heart failure, and for renal protection in patients with diabetes. The doses proposed in this study are well tolerated by non-hypertensive patients without significant effect on blood pressure. The proposed starting dose of losartan is 25 mg orally per day with increase to 50 mg orally per day on day 3 if tolerated until they patient is discharged from the hospital, met stoppage criteria (above) or completed 14 days of therapy.

The most common side effects are fatigue and dizziness. Serious adverse events that are rare include angioedema, hypotension, renal dysfunction or failure, blood dyscrasias, hepatitis, or rhabdomyolysis. The following are meant to mitigate risk to the subjects: Dosing will be done in an inpatient setting with clinically indicated close observations of blood pressure and organ dysfunction (blood work). Subjects with hyperkalemia, renal dysfunction, or who are taking potassium supplements will not be enrolled into the study. Participants will be given written descriptions of potential side effects and potential responses to the side effects.

Sample size and Statistics

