Since there is no information on the effects of losartan in human beings suffering from COVID-19, a statistical analysis based on efficacy is not possible. From a safety perspective, we would accept considering losartan equivalent or superior to the comparison group not receiving losartan (historical or no consent) if there is a $\pm 20\%$ difference in total AE/SAEs. Historical controls will be matched with study participants based on upon age, sex and disease severity in a 2:1 ratio for safety comparison. From a safety perspective, losartan's long track record as a safe medication is reassuring. See section on DSMB for further details on safety monitoring and analysis.

Confidentiality

All information provided by the subject to the investigators, and all information that is collected about the subjects by the investigators, shall be kept confidential to the extent that is provided by law. Computer data files will be stored and backup up to secure, HIPPA compliant, password protected computers and servers. Electronic data capture into REDCap system will be used. Access to these databases will be restricted to individuals associated with the study who require access to the data to perform their duties. These individuals will be named by the principal investigator prior to initiation of the clinical trial. The subject's actual identity cannot be ascertained exclusively from these data and the subject's name shall not be used in any publications. All investigators and staff involved in the research protocol will be bound by this agreement of confidentiality.

Adverse Event and Serious Adverse Event Documentation

Definition of an Adverse Event

For the purpose of this protocol, an AE will be defined as any untoward medical occurrence in a subject during the study listed under DMSB - Anticipated Adverse Events and Grading Scale section of this protocol as well as safety monitoring data listed on table 1 as well as stoppage criteria for losartan.

The event does not necessarily have a causal relationship with the treatment. AEs will be collected for both study groups, treatment and control from the time the ICF is signed until the subject completes study participation.

Definition of a Serious Adverse Event

An SAE is any AE that meets any of the following outcomes:

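### Retrospective controls span the month before the start and the whole study but are matched only on age, sex and severity, so changes in background COVID-19 care can enter the ±20% safety comparison

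*Combined protocol and SAP*

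**What the plan says.** The primary hypothesis is that losartan is safe in acute respiratory failure due to SARS-CoV-2. It is tested in "50 patients with COVID-19 and respiratory failure who meet criteria and agree to participation in the study" (Clinical Trial setup). The decision rule is in Sample size and Statistics: losartan counts as equivalent or superior to a comparison group not receiving it "if there is a $\pm 20\%$ difference in total AE/SAEs". That group may be historical or made up of patients who declined treatment.

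The Control section takes the retrospective controls from patients treated "in the 30 days prior to the study start date (3/25/2020) and during the study period", found by a query of the electronic health record. They are to be "matched with study participants based on upon age, sex and disease severity in a 2:1 ratio for safety comparison". The same section accepts that some controls with exclusion criteria may be needed to reach 2:1.

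On background treatment, inclusion criterion 4 reads "Other concomitant medications such as antivirals and hydroxychloroquine are allowed". The only planned use of this information is a secondary endpoint, "Incidence of medications with possible antiviral activity". No section matches on, stratifies by or adjusts for calendar time or these drugs. Sample size and Statistics refers to the DSMB section for further safety analysis, but that section holds reporting and meeting rules only.

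**The concern.** Every losartan recipient is enrolled on or after the start date, while some controls may precede it. The protocol's own background describes treatment in motion: no approved therapy, and several candidates in trials or about to enter them, none free of side effects. Adverse events are counted whether or not they are causally linked to treatment. A shift in background care can therefore move the event rate without any effect of losartan, and matching on age, sex and severity does not take that shift out.

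The comparison bears directly on the primary hypothesis. If earlier patients had more events, a real excess on losartan could be masked. If they had fewer, losartan could be blamed for a change in care.

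**Working it through.** **No planned figure to reproduce.** The documents give no alpha, power or event rate, so neither the 50 participants nor the ±20% can be derived from them. The margin is not said to be absolute or relative. I read it below as 20 percentage points.

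**Inputs from the documents.** 50 treated; 2:1 matching, hence 2 × 50 = 100 controls; margin 20%.

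**Inputs assumed.** Share of controls from before the start, 25 to 50%; difference in event risk between periods, 10 to 20 points; risk in concurrent controls, 30%.

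**Bias.** In absolute size,

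bias = (early share in controls − early share in treated) × risk difference between periods.

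Taking the early period as strictly pre-study, the treated share is 0:

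- low end: (0.25 − 0) × 0.10 = 0.025, or 2.5 points;
- high end: (0.50 − 0) × 0.20 = 0.10, or 10 points, half of a 20-point margin.

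If the early period also covers the first part of the study, treated patients fall in it too and the bias shrinks. For example, 75% of controls against 50% of treated at 20 points gives (0.75 − 0.50) × 0.20 = 0.05, or 5 points.

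**Effect on the decision.** I took the rule as an observed difference of at most +20 points, with exact binomial probabilities for 50 treated and 100 controls. Suppose that the true excess on losartan is 20 points (50% against 30%) and drift raises the control rate:

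| Upward shift in control rate | Chance of passing |
|---|---|
| none | 52% |
| 2.5 points | 64% |
| 5 points | 74% |
| 10 points | 89% |

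In the other direction, with no true harm (30% on losartan) and controls 10 points lower (20%), the chance of passing falls from 99.5% to 91.5%.

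**Precision if date preference costs controls.** The 95% half-width is 1.96 × √[0.3 × 0.7 × (1/50 + 1/n)], with n the number of controls:

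- n = 100: 1.96 × 0.0794 = 15.6 points;
- n = 75: 1.96 × 0.0837 = 16.4 points;
- n = 50: 1.96 × 0.0917 = 18.0 points.

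The loss is 0.8 to 2.4 points of half-width. A larger sample would recover that loss, but it would not cure the bias.

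**The case against.** The comparison is not purely historical. Retrospective controls also come from the study period, and consenting decliners are followed alongside the treated patients. This stands. It limits the problem, but no rule says how many controls come from each source.

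The pool may already be thin, since the protocol foresees admitting controls with exclusion criteria to reach 2:1. Preferring concurrent patients could draw in more decliners or excluded patients, and so exchange a time bias for a selection bias. This stands as well. A reader might infer that matching on date is free, and for this reason it is not.

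Severity is already matched, and concomitant medication is among the data to be collected, so imbalance could be displayed. This holds only in part. For historical controls the Control section promises only information relating to the safety criteria, so baseline scores and drug use cannot be assumed to be extracted for them.

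Two stronger readings are tempting. One is that the allowed drugs cause the laboratory events graded in Table 1. The documents do not say so, and the point needs only that background care may have changed. The other is that the bias could fill most of the margin. That would require, for example, three quarters of the controls to come from one 30-day window, for which the documents give no basis.

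**Conclusion.** The gap is real and lies in the comparison behind the primary hypothesis: controls from before and during the study are pooled, and nothing accounts for when they were treated. Bias is possible, but it is not demonstrated. Under the assumed inputs it is 2.5 to 10 points, in either direction, and its relation to the margin depends on reading ±20% as absolute. The documents do not support a claim that the comparison is biased by a known amount or in favour of losartan. The change is worth making because it is cheap and the assumed bias mostly exceeds the precision given up. It does not put the trial's conduct in question.

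**What to change.** Change the matching and analysis text as follows.

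1. Among controls that match on age, sex and severity, choose the closest admission date and prefer study-period controls to pre-study ones. Set no strict caliper, so that no control need be lost, and state what happens if 2:1 cannot be reached.
2. Define an index day for controls, for example the first day on which all inclusion criteria are met. Day 0 is an enrolment day, and adverse events are counted from consent. Retrospective controls have neither. Select matches from data up to the index day, before adverse-event data are extracted.
3. Report the adverse-event comparison with concurrent controls only as a sensitivity analysis, and by source: pre-study, concurrent retrospective, decliner.
4. Extract antiviral and adjunctive drug use on the index day for controls and show its balance against treated patients at Day 0. Adjust if it is imbalanced and event numbers allow. Later use should not be adjusted for.

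The cost is protocol or SAP wording and some extra extraction. Admission date should be retrievable from the health-record query, but index-day drug use must be named as an item to collect. Matches on the other factors may be slightly looser, and the sensitivity analysis may run at a lower ratio with the precision loss shown above. The report should state how many concurrent controls were decliners or had exclusion criteria.
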